#### **4.7.4 Vital Signs**

Vital signs (absolute values and change from baseline) will be summarized by treatment arm over time without any replacement for missing data.

#### **4.7.5 ECGs**

Incidence of clinically significant ECG abnormalities will be reported in patient listings. ECG absolute values and change from baseline will be summarized by treatment arm. ECG QT interval and QT interval with Fridericia's correction will also be summarized.

ECGs will also be analysed in combination with the PK data (area under the concentration–time curve [AUC] and  $C_{max}$ ) to assess the relationship between study drug plasma concentrations (AUC and  $C_{max}$ ) and correct QT interval duration.

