#### **4.5.11 Electrocardiograms**

Triplicate ECG recordings will be obtained at specified timepoints, as outlined in the Schedule of Assessments ([Appendix 1](#) and [Appendix 2](#)). Additional ECG recordings may be performed at unscheduled timepoints as clinically indicated. Please note that the time points of ECG recordings are matched to PK sampling time points and should be performed sequentially as indicated in Section 4.5.10.

All ECG recordings must be performed using a standard high-quality, high-fidelity digital electrocardiograph machine equipped with computer-based interval measurements. Lead placement should be as consistent as possible. ECG recordings must be performed after the patient has been resting in a supine position for at least 10 minutes. All ECGs are to be obtained prior to other procedures scheduled at that same time (e.g., vital sign measurements, blood draws). Circumstances that may induce changes in heart rate, including environmental distractions (e.g., television, radio, conversation) should be avoided during the pre-ECG resting period and during ECG recording.

For safety monitoring purposes, the investigator or designee must review, sign, and date all ECG tracings. Paper copies of ECG tracings will be kept as part of the patient's permanent study file at the site. The following should be recorded in the appropriate eCRF: ECG abnormality (including waveform), heart rate; PQ, PR, RR, QRS intervals; QT interval and corrected QTcF interval based on the machine readings of the individual ECG tracings. Any morphologic waveform changes or other ECG abnormalities must be documented on the eCRF.

If at a particular postdose timepoint the mean QTcF is > 500 ms and/or 60 ms longer than the baseline value, another ECG must be recorded, ideally within the next 5 minutes, and ECG monitoring should continue until QTcF has stabilized on two successive ECGs. The investigator should also evaluate the patient for potential concurrent risk factors (e.g., electrolyte abnormalities, co-medications known to prolong the QT interval, severe bradycardia) and provide this information to the eCRF. In case a patient presents with an episode of grade  $\geq 2$  supraventricular arrhythmia (atrial fibrillation, atrial flutter, sinus tachycardia, etc.), an unscheduled ECG should be recorded. Standard-of-care treatment may be instituted per the discretion of the

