## 6.9 PHARMACOKINETIC ANALYSES

Key PK parameter values (CL/F and Vd/F) of idasanutlin and cytarabine (CL and Vd) will be estimated using a popPK approach. The influence of covariates such as gender, race/ethnicity, weight, hematological parameters at baseline, renal/hepatic impairment, and degree of underlying disease will be investigated. Other PK parameters such as  $C_{max}$ ,  $C_{trough}$ ,  $AUC_{0-\tau}$ ,  $AUC_{0-24h}$ , and  $t_{1/2}$  will be derived from the individual post hoc predictions. Details of the population analysis will be described in the Modeling and Simulation Analysis Plan. Results of this analysis will be reported separately.

If appropriate, an exploratory PK/pharmacodynamic analysis may be performed post hoc. The primary focus will be exploration of the relationship between measures of exposure to idasanutlin in combination with cytarabine ( $C_{max}$ ,  $C_{trough}$ , and  $AUC_{0-24h}$ ) and ECG, drug-related adverse effects as well as clinical efficacy parameters.

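### SAP 4.7.5 relates corrected QT only to AUC and Cmax and leaves the time-matched ECG and PK samples without a planned model, so a small exposure effect could be missed

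*SAP*

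**What the plan says.** SAP 4.7.5 has two parts. The first is descriptive: "ECG absolute values and change from baseline will be summarized by treatment arm". The second is the exposure analysis: "ECGs will also be analysed in combination with the PK data" "to assess the relationship between study drug plasma concentrations" and corrected QT, with AUC and Cmax named in brackets as the exposure measures. It does not say which ECG value is paired with them, what model is fitted, how baseline is handled, or whether placebo patients are included.

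Protocol 6.9 is similar. Cmax, Ctrough and AUC0-24h are listed against ECG, and such parameters "will be derived from the individual post hoc predictions" of the population PK model. The analysis is optional there: "If appropriate, an exploratory PK/pharmacodynamic analysis may be performed post hoc".

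The data collection is richer. Protocol 4.5.11 requires triplicate recordings and states that "the time points of ECG recordings are matched to PK sampling time points and should be performed sequentially". Appendices 1 and 2 give the same seven Cycle 1 times for ECG and PK: Day 1 predose, end of cytarabine infusion and 6 hours; Day 2 predose; Day 5 predose, end of infusion and 6 hours. ECGs are taken in both arms. Placebo PK samples are drawn to protect the blind but not assayed (protocol 4.5.10.1).

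**The concern.** AUC belongs to no single ECG time, and a model-predicted Cmax can fall between recordings. If each patient is reduced to one exposure value, the analysis loses the within-patient rise in concentration from Day 1 to Day 5. With a half-life of about one day and twice-daily dosing, that rise is large. Unless placebo patients are given zero exposure, they have no value to enter.

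QT is a monitored risk in this trial: there is a QTcF exclusion limit, a list of prohibited drugs and an action threshold. Protocol 1.2.2.2 reports that Phase I saw no correlation between concentration and QTcF. This larger, placebo-controlled trial could test that properly, but an insensitive analysis might only repeat the null result.

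**Working it through.** The documents state no sample size, variance, target slope or power for the QT analysis, so there is no figure of theirs to reproduce. The size of the loss has to be simulated.

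**Inputs from the documents**
- Arms: 440 × 2/3 = 293 idasanutlin and 440 × 1/3 = 147 placebo, as in SAP 3.1.
- PK variability: about 50% between patients and 26% within patients; half-life about 1 day (protocol 1.2.2.1).
- Six post-baseline matched times in Cycle 1.

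**Assumed, because the documents give nothing:** one-compartment PK; a linear effect; between-patient SD of the QTcF change 5 to 15 ms; residual SD 8 to 15 ms; patient-by-day SD 0 or 8 ms; 20% error in predicted AUC and Cmax; two-sided 5% test. The true effect is expressed in ms at the geometric-mean Day 5 (6-hour) concentration. In this PK model, mean concentrations at the six times, relative to Day 5 at 6 hours, are 0.24, 0.30, 0.43, 0.81, 1.03 and 1.00.

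**Analyses compared**
- Patient-level: ordinary regression of Day 5 change in QTcF on Day 5 Cmax or AUC, idasanutlin arm only.
- The AUC regression with placebo patients entered at zero exposure.
- Time-matched: change in QTcF on concentration at that time (placebo 0), time point and arm, with a random patient intercept. Baseline QTcF was not in the simulated model.

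Information share = (SE time-matched / SE patient-level)², at zero slope. In the central case (between-patient SD 10, residual SD 12, no patient-by-day noise) the SEs are 2.06 ms (Cmax), 1.85 ms (AUC) and 0.84 ms (time-matched). The shares are (0.84/2.06)² = 17% and (0.84/1.85)² = 21%, and the SE ratios are 2.45 and 2.20.

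Power to detect a 5 ms effect:

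| SDs: between / residual / patient-by-day (ms) | Share, active only | Cmax, active only | AUC, active only | AUC, placebo at 0 | Time-matched |
|---|---|---|---|---|---|
| 10 / 12 / 0 | 17–21% | 48% | 53% | 97% | about 100% |
| 10 / 12 / 8 | 28–30% | 39% | 40% | 84% | 92% |
| 10 / 8 / 0 | 12–13% | 71% | 75% | 100% | 100% |
| 10 / 8 / 8 | 27–28% | 53% | 57% | 95% | 98% |

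- At 3 ms, central case: 20 to 26% active only, against 92% time-matched.
- At 10 ms: 77 to 100% for the Day 5 active-only analyses in all settings. Regressing the mean of all six ECGs on AUC does worse, at 39 to 97%.
- Across all settings the active-only analyses keep 12 to 38% of the information, and the version with placebo at zero keeps 31 to 77%.
- Active-only slopes averaged about 3.8 to 4.0 for a true 5 ms in most settings.

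**Second simulation.** This one also had the arm in the model, 26% within-patient variability and 20% AUC error, and added an 8 ms Day 5 shift to both arms. The time-matched SE was 0.53 to 1.24 ms with no bias. Active-only Day 5 AUC gave 0.71 to 1.68 ms, with slopes of about 4.0 to 4.3 for a true 5. The information gain was about 1.5 to 4.4 times, so the SE ratio was √1.5 = 1.2 to √4.4 = 2.1.

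Together, the SE ratio runs from about 1.2 (second simulation) to 2.45 (central case of the first). The lowest share, 12%, would give 1/√0.12 = 2.9. That comes from a low-noise setting in which power at 5 ms is already 71%.

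**The case against.** **The analysis may be better than its description.** The active-only, one-value-per-patient regression is inferred from the metrics named; the SAP does not state it. A reader might infer that placebo patients contribute nothing and that only a small part of the information is used. The documents do not support that as a fact. Placebo can enter at zero exposure, and most of the loss of precision then goes, although attenuation remains. SAP 4.6 also defers PK details to a Modeling and Simulation Analysis Plan that is not in the package and may contain a concentration-QTc model. This stands. However, SAP 4.7.5 does not point to that plan, and protocol 6.9 describes it as covering the population PK analysis.

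**Common shifts.** A reader might also infer that a QT change between Day 1 and Day 5 common to both arms, for example from electrolyte loss or supportive drugs, could not be separated from drug. That is wrong for a Day 5 regression, where a common shift goes into the intercept. With 8 ms added to every patient on Day 5, the Day 5 slope averaged 5.06 for a true 5. The by-arm summaries also show such a shift, since they include placebo ECGs.

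**Low stakes.** The exposure analysis is exploratory, protocol 6.9 makes it optional, and no decision rule uses it. The QTcF action thresholds in protocol 4.5.11 operate without it. This stands and limits the weight of the point.

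**Conclusion.** The point holds as an inexpensive improvement to an exploratory safety analysis. The trial gathers time-matched ECG and PK data with a placebo arm, and neither document commits to a model that uses the pairing. The loss in precision and the attenuation apply if the plan is carried out as an active-arm, patient-level regression. The practical risk is confined to small effects of about 3 to 5 ms. Even a Day 5 patient-level analysis would usually find 10 ms or more.

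The direction was the same in every setting tried. The size rests on QTc variances, a PK structure and a linear effect that the documents do not supply, so the ratio of 1.2 to 2.5 is a range under assumptions. The SAP's silence on placebo patients matters as much as the choice of metric: in the two settings with residual SD 12 ms, it alone moves power at 5 ms for the AUC regression from 40–53% to 84–97%.

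**What to change.** In SAP 4.7.5, make the exposure-QTc analysis a linear mixed model of change from baseline in QTcF at each matched Cycle 1 time on the idasanutlin concentration at that time, set to zero for placebo patients. Include time point, treatment arm and baseline QTcF as fixed effects, with patient random effects. Report the model-predicted placebo-adjusted difference at the Day 5 peak concentration (arm term plus slope times that concentration) with a 90% CI. Keep the AUC and Cmax analyses as supportive, and state which ECG value they use and whether placebo enters at zero.

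If the Modeling and Simulation Analysis Plan already specifies such a model, citing its section in SAP 4.7.5 is enough.

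The cost is a paragraph of SAP text and one additional exploratory model. No new samples, assays or ECGs are needed.

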### **4.8 PATIENT-REPORTED OUTCOMES**

The PRO-evaluable population will include all randomized patients who have a baseline and at least one post-baseline PRO assessment. The PRO-evaluable population will be used for descriptive analyses of visit summary and change from baseline, and responder analyses. All TP53 WT randomized patients will be used for completion analyses and time-to-event (improvement/deterioration) analyses. All PRO analyses will be performed based on the treatment arm assigned at randomization.

#### **4.8.1 EORTC QLQ-C30**

The EORTC QLQ-C30 is composed of both multi-item and single-item scales scored 0 to 100. Scoring for the EORTC QLQ-C30 questionnaire will be based on the EORTC guidelines (Fayers et al. 2001). Consistent with the EORTC guidelines, prorated scores will be computed for a multi-item scale if more than 50% of the constituent items have been completed for that scale. For multi-item scales with less than 50% of the items completed, the scale will be considered as missing. Values for missing single-item scales will not be imputed.

Completion analysis will be performed for the overall EORTC QLQ-C30 questionnaire. The number and proportion of patients who completed the EORTC QLQ-C30 questionnaire will be summarized by treatment arm and for each time point. The completion rate will be based on the number of patients expected to complete the questionnaire at a particular time point, that is, those patients who had the opportunity to complete the EORTC QLQ-C30 questionnaire.

Visit summary and change from baseline analyses will be performed for all scales of the EORTC QLQ-C30. Summary statistics (number of patients, mean, standard deviation, median, minimum, maximum) of scores and change from baseline to each time point will be presented by treatment arm. Plots of mean change from baseline will be generated for EORTC QLQ-C30 physical functioning, fatigue, and global health status/QoL scales. In addition, for the subset of patients receiving HSCT, physical functioning and fatigue will be descriptively summarized at their last visit prior to transplant.

For responders' analysis, the number and proportion of patients with a clinically meaningful improvement (as defined below), deterioration, or who remained stable will be summarized by treatment arm, for the EORTC QLQ-C30 physical functioning, fatigue, and global health status/QoL scales. The 95% CI around the proportion will be calculated using the Clopper-Pearson method for each treatment arm. These will be calculated at Cycle 1 Day 28, Cycle 2 Day 28, Cycle 3 Day 28, and at treatment discontinuation

For physical function and global health status/QoL, higher scores are reflective of better HRQoL and a clinically meaningful improvement is defined as at least a 10-point increase. For fatigue, lower scores are reflective of less fatigue and a clinically meaningful improvement is defined as at least a 10-point decrease. Conversely, clinically meaningful deterioration is defined as at least a 10-point decrease and 10-point increase, respectively.

Time to deterioration is defined as the time from randomization to the first documentation of a 10-point decrease in EORTC QLQ-C30 physical functioning and global health status and a 10-point increase in fatigue from baseline. Time to

improvement is defined as the time from randomization to the first documentation of a 10-point increase in EORTC QLQ-C30 physical functioning and global health status and a 10-point decrease in fatigue from baseline.

Time to deterioration and time to improvement will be displayed using Kaplan Meier curves. Patients who do not have an observed deterioration or improvement, respectively, at the time of clinical data cut-off will be censored at the last non-missing assessment date. Patients without a post-baseline assessment will be censored at randomization.

The EQ-5D-5L questionnaire consists of two components: the EQ-5D-5L descriptive system, which has 5 dimensions (mobility, self-care, usual activities, pain/discomfort, and anxiety/depression) with five levels (no problems, slight problems, moderate problems, severe problems, and extreme problems) and a visual analogue scale (EQ VAS) ranging from 0 (worst possible health state) to 100 (best possible health state), which measures an overall health state.

The EQ-5D-5L health states, which are defined based on the EQ-5D-5L descriptive system, will be converted into a single index value according to the EQ-5D-5L guidelines ([van Reene and Janssen 2015](#)). The EQ-5D-5L single index value will be calculated using the United Kingdom preference weights. Descriptive statistics (mean, standard deviation, median, minimum, and maximum) and change from baseline will be presented by treatment arm and at each timepoint.

Data from the EQ-VAS will be used to assess the overall health status. Descriptive statistics (mean, standard deviation, median, minimum, and maximum) and change from baseline at each timepoint will be displayed by treatment arm.

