#### **Within the all-patient population**

- To assess the safety of idasanutlin plus cytarabine as compared with cytarabine and placebo
- To characterize the pharmacokinetics of both idasanutlin and cytarabine
- To compare the differences in disease and treatment related symptoms and health-related quality of life between treatment arms

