## 6.10 PATIENT-REPORTED OUTCOME ANALYSES

Scoring for the EORTC QLQ-C30 questionnaire will be based on the scoring manual. Consistent with the user manual, prorated scores will be computed for a subscale if more than 50% of the constituent items have been completed for that subscale. For subscales with less than 50% of the items completed, the subscale will be considered as missing.

Summary statistics of the EORTC QLQ-C30 scales and their changes from baseline will be calculated at each assessment timepoint for both study arms. Analysis details of these PROs will be provided in the Statistical Analysis Plan.

Health utility scores, as assessed by the EQ-5D-5L, will be evaluated for patients with a baseline assessment and at least one post-baseline EQ-5D-5L assessment that generate a score. Scores at baseline and change from baseline scores for each timepoint will be quantified using descriptive statistics. The results will be used for more complete health economic data analysis.

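### Comparing HRQoL between arms is a secondary objective, but SAP 4.8.1 specifies no between-arm estimate for any patient-reported outcome

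*SAP*

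**What the plan says.** Protocol 2.2 lists this secondary objective for the all-patient population: "To compare the differences in disease and treatment related symptoms and health-related quality of life between treatment arms". The same objective appears for the TP53 WT population.

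Protocol 6.10 answers it with description: "Summary statistics of the EORTC QLQ-C30 scales and their changes from baseline will be calculated at each assessment timepoint for both study arms". It leaves further detail to the SAP.

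SAP 4.8.1 then gives, for the EORTC QLQ-C30:

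- **Scores and changes.** Number, mean, SD, median, minimum and maximum "of scores and change from baseline to each time point will be presented by treatment arm", with mean-change plots for physical functioning, fatigue and global health status.
- **Responder categories.** The SAP summarises "the number and proportion of patients with a clinically meaningful improvement (as defined below), deterioration, or who remained stable" for those three scales at Day 28 of Cycles 1, 2 and 3 and at treatment discontinuation. For physical functioning and global health status, "a clinically meaningful improvement is defined as at least a 10-point increase"; the direction is reversed for fatigue, and deterioration mirrors improvement. "The 95% CI around the proportion will be calculated using the Clopper-Pearson method for each treatment arm".
- **Time to event.** "Time to deterioration and time to improvement will be displayed using Kaplan Meier curves". No hazard ratio or test is named.

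For EQ-5D-5L the same section gives descriptive statistics by arm only. Under SAP 4.8 the visit-level analyses use a PRO-evaluable subset of all randomised patients, while the time-to-event displays use all randomised TP53 WT patients.

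**The concern.** The objective asks for a comparison, and the analysis stops at two columns of summaries. If the SAP is followed exactly, the study report will contain no estimate of the difference between arms in any patient-reported outcome and no statement of its precision.

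This matters because the effect could go either way. Protocol 5.1.1.1 reports diarrhoea in more than 90% of patients in the Phase I AML study, so a cost in quality of life is plausible. The design also assumes that the CR rate roughly doubles, so a benefit is plausible too. The three main scales run from 0 to 100, have a baseline value, and are collected at Cycle 1 Days 8, 15 and 28 (Protocol 4.5.12). At each visit the plan attaches an interval only after the score has been cut at 10 points, and then only within an arm.

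**Working it through.** **1. Is there a between-arm PRO estimate anywhere?** I set the planned methods side by side.

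| Endpoint | Where | Between-arm method |
|---|---|---|
| OS | SAP 4.4.1 | Stratified log-rank test, stratified Cox HR with 95% CI |
| CR, ORR, HSCT | SAP 4.4.2 | Stratified Cochran-Mantel-Haenszel test |
| EFS, DOR | SAP 4.4.2 | As for OS |
| QLQ-C30 scores and changes | SAP 4.8.1 | None |
| QLQ-C30 10-point categories | SAP 4.8.1 | None (Clopper-Pearson CI per arm) |
| QLQ-C30 time to deterioration or improvement | SAP 4.8.1 | None (Kaplan-Meier display) |
| EQ-5D-5L index and VAS | SAP 4.8.1 | None |

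PROs are also absent from the 11-step sequence in SAP 4.4.2.

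**2. Is there a rule for a missing visit score or a death?** SAP 4.10 refers to Section 4.8 for PROs. That section covers proration within a scale and censoring for the time-to-event displays. It says nothing about a form missing at a visit or a patient who dies before it.

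**3. How much could an adjusted difference add?** The plan states no PRO power, SD or effect, so there is no figure to reproduce. All inputs here are assumptions: 200 vs 100 evaluable at Cycle 1 Day 28 (about 80% of the planned 374 TP53 WT patients, 2:1), SD 20 or 25, baseline correlation r 0.4 or 0.6, control mean change -5, idasanutlin worse by d = 6, 8 or 10 points, two-sided 5%, normal scores.

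- Adjusted difference: SD_adj = SD·√(1 - r²); SE = SD_adj·√(1/200 + 1/100); power = Φ(d/SE - 1.96).
- 10-point cut: SD_chg = SD·√(2(1 - r)); p_control = Φ((-10 + 5)/SD_chg); p_ida = Φ((-10 + 5 + d)/SD_chg); then a two-proportion test with pooled variance under the null.

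Example with d = 8, SD 25, r 0.4:

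- Adjusted difference: SD_adj = 22.91, SE = 2.806, power = Φ(2.851 - 1.960) = 81.3%.
- 10-point cut: SD_chg = 27.39, p = 0.428 vs 0.544, null SE 0.0612, alternative SE 0.0607, power = Φ((0.116 - 1.96 × 0.0612)/0.0607) = 47.4%.

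| d | SD | r | p control | p ida | Power, adjusted (%) | Power, 10-point cut (%) | Gain (points) |
|---|---|---|---|---|---|---|---|
| 6 | 25 | 0.4 | 0.428 | 0.515 | 57.1 | 29.4 | 27.7 |
| 6 | 25 | 0.6 | 0.412 | 0.518 | 68.8 | 41.1 | 27.7 |
| 6 | 20 | 0.4 | 0.410 | 0.518 | 76.2 | 42.5 | 33.7 |
| 6 | 20 | 0.6 | 0.390 | 0.522 | 86.5 | 58.2 | 28.3 |
| 8 | 25 | 0.4 | 0.428 | 0.544 | 81.3 | 47.4 | 34.0 |
| 8 | 25 | 0.6 | 0.412 | 0.553 | 90.4 | 64.1 | 26.3 |
| 8 | 20 | 0.4 | 0.410 | 0.554 | 94.6 | 65.9 | 28.7 |
| 8 | 20 | 0.6 | 0.390 | 0.567 | 98.3 | 82.7 | 15.6 |
| 10 | 25 | 0.4 | 0.428 | 0.572 | 94.6 | 66.0 | 28.6 |
| 10 | 25 | 0.6 | 0.412 | 0.588 | 98.3 | 82.8 | 15.5 |
| 10 | 20 | 0.4 | 0.410 | 0.590 | 99.4 | 84.3 | 15.0 |
| 10 | 20 | 0.6 | 0.390 | 0.610 | 99.9 | 95.4 | 4.5 |

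Gains are taken before rounding and run from about 5 to 34 points.

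**4. Why Cycle 1 Day 28?** Later cycles are reached mainly by responders (Protocol 4.3.2.4). If only complete responders continued, Cycle 2 in TP53 WT patients would hold about 0.16 × 374/3 = 20 control and 0.323 × 374 × 2/3 = 81 idasanutlin patients, selected by outcome. A mean difference there is not a clean randomised comparison.

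**The case against.** The strongest reply is that descriptive PRO reporting is a consistent choice. Protocol 6.10 and SAP 4.8.1 agree, PROs carry no alpha, and no claim rests on them. Means and SDs of change are given by arm for every scale at every timepoint, so a reader can derive an unadjusted difference and its interval. The Kaplan-Meier curves also show the arms together. All of this is true, and it keeps the point minor. It does not meet the objective, which is worded as a comparison in both populations. A difference worked out afterwards by a reader is neither pre-specified nor baseline-adjusted.

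A second reply is that an adjusted mean without a rule for death has no clear estimand. That stands. Early death is expected often enough to have its own stopping criteria (SAP 4.11.2). The rule therefore has to be part of the fix.

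A reader might also infer that the responder analysis costs the trial a definite amount of power. The documents do not support that. No PRO test is planned, so no planned power is lost, and every input to the table above is assumed. A wider grid of assumptions gives differences from 0 to about 50 points.

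**Conclusion.** The point holds as a gap between objective and analysis: a secondary objective to compare HRQoL has no between-arm estimate in either document. This follows from the text and needs no assumption. It is a desirable improvement, with no effect on the primary analysis or on type I error.

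The 5-34 point range illustrates why the full score, adjusted for baseline, is the better basis for the missing estimate. It depends on the assumed evaluable numbers, SD, correlation, control change and effect. It is smallest where the 10-point cut already has about 95% power. It does not measure any deficiency in a planned test.

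**What to change.** In SAP 4.8.1, for physical functioning, fatigue and global health status at Cycle 1 Day 28:

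- Pre-specify a between-arm mean difference with 95% CI from a linear model, or an MMRM over Cycle 1 Days 8, 15 and 28, adjusted for baseline score and the randomisation factors.
- Estimate it in the TP53 WT population and repeat it in all patients, matching the two objectives. Keep it outside the testing hierarchy.
- State how deaths before Day 28 and missing forms are handled. One option is an estimate among patients alive, with a sensitivity analysis that ranks death as the worst outcome.
- Keep the 10-point proportions and the Kaplan-Meier displays as descriptive aids to interpretation.

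The cost is a little more analysis on data already scheduled for collection, and agreement on one missing-data rule. No alpha changes. Protocol 6.10 already leaves the analysis detail to the SAP, so the change can be made there.
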